6.6 Pharmacodynamics (Not applicable)

6.7 Pharmacogenetics (Not applicable)

6.8 Health economics (Not applicable)

7. BIOLOGICAL SAMPLING PROCEDURES

7.1 Volume of blood

The maximum volume of blood that will be taken for any given patient for the purposes of the study will typically not exceed 215 mL.

The total volume of blood that will be drawn from each patient in this study is shown in Table 10.

Table 10 Volume of blood to be drawn from each patient: Parts A and B

Assessment		Sample volume (mL)	No. of samples A ^a	B ^b	Follow-up	Total volume (mL)
Safety	Clinical chemistry	2.7	3	12	0	40.5
	Clinical chemistry ^c	3.5	0	7	1	28.0
	Haematology	2.7	3	19	1	62.1
	RBC folate	2.0	0	7	1	16.0
Pharmacokinetic	Olaparib	4.0	15	0	0	60.0
	Olaparib protein binding	3.0	1	0	0	3.0
Total volume (mL)			79.2	122.2	8.2	209.6

^a Includes screening/baseline blood volumes.

^b Number of samples in Part B is based on a patient being in the study for an estimated maximum of 15 months.

^c Includes TSH, vitamin B12 and folate (to be performed on Day 1, then monthly for the first 6 months, at discontinuation and at the 30-day follow-up visit).

Note: Table is for guidance. Exact blood volumes may differ depending on local requirements.

7.2 Handling, storage and destruction of biological samples

The samples will be used up or disposed of after analyses or retained for further use as described here.

7.2.1 Pharmacokinetic samples

Pharmacokinetic samples will be disposed of after finalisation of the Bioanalytical Report or 6 months after issuing the draft Bioanalytical Report (whichever is earlier), unless requested for future analyses.

Pharmacokinetic samples may be disposed of or destroyed or anonymised by pooling. Additional analyses may be conducted on the anonymised, pooled PK samples to further evaluate and validate the analytical method. Any results from such analyses may be reported separately from the CSR. Anonymised samples will be retained for no more than 5 years after the CSR is finalised.

Incurred sample reproducibility analysis, if any, will be performed alongside the bioanalysis of the test samples. The results from the evaluation will not be reported in the CSR, but separately in a Bioanalytical Report.

7.3 Labelling and shipment of biohazard samples

The PI ensures that samples are labelled and shipped in accordance with the Laboratory Manual and the Biological Substance, Category B Regulations (materials containing or suspected to contain infectious substances that do not meet Category A criteria), see [Appendix C](#) 'International Airline Transportation Association (IATA) 6.2 Guidance Document'.

Any samples identified as Infectious Category A materials are not shipped and no further samples will be taken from the patient unless agreed with AstraZeneca or its representative and appropriate labelling, shipment and containment provisions are approved.

7.4 Chain of custody of biological samples

A full chain of custody is maintained for all samples throughout their lifecycle.

The PI keeps full traceability of collected biological samples from the patients while in storage at the study site until shipment or disposal (where appropriate) and keeps documentation of receipt of arrival.

The sample receiver keeps full traceability of the samples while in storage and during use until used or disposed of or until further shipment and keeps documentation of receipt of arrival.

Quintiles keeps oversight of the entire life cycle through internal procedures, monitoring of study sites, and auditing of external laboratory providers.

7.5 Withdrawal of informed consent for donated biological samples

If a patient withdraws consent to the use of donated biological samples, the samples will be disposed of/destroyed, and the action documented. If samples are already analysed, AstraZeneca is not obliged to destroy the results of this research.

As collection of the biological samples is an integral part of the study, then the patient is withdrawn from further study participation if consent is withdrawn.

The PI:

- Ensures patients' withdrawal of informed consent to the use of donated samples is notified immediately to AstraZeneca or its representative
- Ensures that biological samples from that patient, if stored at the study site, are immediately identified, disposed of/destroyed, and the action documented
- Ensures the laboratory(ies) holding the samples is/are informed about the withdrawn consent immediately and that samples are disposed/destroyed, the action documented and the signed document returned to the study site
- Ensures that the patient and AstraZeneca or its representative are informed about the sample disposal.

AstraZeneca or its representative ensures the central and bioanalytical laboratories holding the samples are informed about the withdrawn consent immediately and that samples are disposed of/destroyed and the action documented and returned to the study site.

8. ETHICAL AND REGULATORY REQUIREMENTS

8.1 Ethical conduct of the study

The study will be performed in accordance with ethical principles that have their origin in the Declaration of Helsinki and are consistent with International Conference on Harmonisation (ICH)/Good Clinical Practice (GCP), applicable regulatory requirements and the AstraZeneca policy on Bioethics and Human Biological Samples.

8.2 Patient data protection

The Informed Consent Form will incorporate (or, in some cases, be accompanied by a separate document incorporating) wording that complies with relevant data protection and privacy legislation.

8.3 Ethics and regulatory review

An Ethics Committee (EC) should approve the final study protocol, including the final version of the Informed Consent Form and any other written information and/or materials to be provided to the patients.

The investigator will ensure the distribution of these documents to the applicable EC and to the study site staff.

The opinion of the EC should be given in writing. The investigator should submit the written approval to AstraZeneca or its representative before enrolment of any patient into the study.

The EC should approve all advertising used to recruit patients for the study.

AstraZeneca or its representative should approve any modifications to the Informed Consent Form that are needed to meet local requirements.

If required by local regulations, the protocol should be re-approved by the EC annually.

Before enrolment of any patient into the study, the final study protocol, including the final version of the Informed Consent Form, is approved by the National Regulatory Authority or a notification to the National Regulatory Authority is done, according to local regulations.

AstraZeneca or its representative will handle the distribution of any of these documents to the National Regulatory Authorities.

AstraZeneca or delegate will provide Regulatory Authorities, ECs and PIs with safety updates/reports according to local requirements.

AstraZeneca or its representative will be responsible for informing the Regulatory Authorities of SAEs/suspected unexpected serious adverse reactions (SUSARs) as per the European Union (EU) Clinical Trial Directive and/or local country regulations and guidelines.

8.4 Informed consent

The PI at each site will:

- Ensure each patient is given full and adequate oral and written information about the nature, purpose, possible risk and benefit of the study
- Ensure each patient is notified that they are free to discontinue from the study at any time
- Ensure that each patient is given the opportunity to ask questions and allowed time to consider the information provided
- Ensure each patient provides signed and dated informed consent before conducting any procedure specifically for the study

- Ensure the original, signed Informed Consent Form(s) is/are stored in the Investigator's Study File
- Ensure a copy of the signed Informed Consent Form is given to the patient
- Ensure that any incentives for patients who participate in the study as well as any provisions for patients harmed as a consequence of study participation are described in the informed consent form that is approved by an EC.

8.5 Changes to the protocol and informed consent form

Study procedures will not be changed without the mutual agreement of the co-ordinating investigator and AstraZeneca.

If there are any substantial changes to the study protocol, then these changes will be documented in a study protocol amendment and where required in a new version of the study protocol (Revised Clinical Study Protocol).

The amendment is to be approved by the relevant EC and if applicable, also the National Regulatory Authority, before implementation. Local requirements are to be followed for revised protocols.

AstraZeneca or its representative will distribute any subsequent amendments and new versions of the protocol to each PI. For distribution to EC see Section [8.3](#).

If a protocol amendment requires a change to a study site's Informed Consent Form, AstraZeneca and the study site's EC are to approve the revised Informed Consent Form before the revised form is used.

If local regulations require, any administrative change will be communicated to or approved by each EC.

8.6 Audits and inspections

Authorised representatives of AstraZeneca or its representative, a Regulatory Authority, or an EC may perform audits or inspections at the study site, including source data verification. The purpose of an audit or inspection is to systematically and independently examine all study-related activities and documents, to determine whether these activities were conducted, and data were recorded, analysed, and accurately reported according to the protocol, GCP guidelines of the ICH, and any applicable regulatory requirements. The investigator will contact AstraZeneca or its representative immediately if contacted by a regulatory agency about an inspection at the study site.

9. STUDY MANAGEMENT BY ASTRAZENECA

This study will be managed by Quintiles, on behalf of AstraZeneca, and Quintiles will act as the AstraZeneca representatives.

9.1 Pre-study activities

Before the first patient is entered into the study, it is necessary for a representative of AstraZeneca to visit the investigational study site to:

- Determine the adequacy of the facilities
- Determine availability of appropriate patients for the study
- Discuss with the investigator(s) (and other personnel involved with the study) their responsibilities with regard to protocol adherence, and the responsibilities of AstraZeneca or its representatives. This will be documented in a CSA between AstraZeneca and the investigator.

9.2 Training of study site personnel

Before the first patient is entered into the study, an AstraZeneca representative will review and discuss the requirements of the Clinical Study Protocol and related documents with the investigational staff and also train them in any study specific procedures and system(s) utilised.

The PI will ensure that appropriate training relevant to the study is given to all of these staff, and that any new information relevant to the performance of this study is forwarded to the staff involved.

The PI will maintain a record of all individuals involved in the study (medical, nursing and other staff).

9.3 Monitoring of the study

During the study, an AstraZeneca representative will have regular contacts with the study site, including visits to:

- Provide information and support to the investigator(s)
- Confirm that facilities remain acceptable
- Confirm that the investigational team is adhering to the protocol, that data are being accurately and timely recorded in the CRFs, that biological samples are handled in accordance with the Laboratory Manual and that IP accountability checks are being performed

- Perform source data verification (a comparison of the data in the CRFs with the patient's medical records at the hospital or practice, and other records relevant to the study) including verification of informed consent of participating patients. This will require direct access to all original records for each patient (eg, clinic charts)
- Ensure withdrawal of informed consent to the use of the patient's biological samples is reported and biological samples are identified and disposed of/destroyed accordingly, and the action is documented, and reported to the patient.

The AstraZeneca representative will be available between visits if the investigator(s) or other staff at the study site needs information and advice about the study conduct.

9.3.1 Source data

Refer to the CSA for location of source data.

9.4 Study agreements

The PI at each study site should comply with all the terms, conditions, and obligations of the CSA for this study. In the event of any inconsistency between the protocol and the CSA, the terms of this protocol shall prevail with respect to the conduct of the study and the treatment of patients and in all other respects, not relating to study conduct or treatment of patients, the terms of the CSA shall prevail.

Agreements between AstraZeneca or its representative and the PI should be in place before any study-related procedures can take place, or patients are enrolled.

9.4.1 Archiving of study documents

The Investigator follows the principles outlined in the CSA.

9.5 Study timetable and end of study

The end of Part A of this study is defined as either the 30-day follow-up date of the last patient to discontinue after Part A OR the date of the last patient in (LPI) into Part B, whichever is the later.

The end of Part B of this study is defined as the date when all patients receiving olaparib in Part B have been followed for a period of at least 12 months since the last patient entered Part B (defined as date of LPI in Part B plus 12 calendar months). At this time point, the clinical study database will close to new data. Patients are, however, permitted to continue to receive olaparib beyond the closure of the database if, in the opinion of the investigator, they are continuing to receive benefit from treatment with olaparib. For patients who do continue to receive treatment beyond the closure of the database, investigators will continue to report all SAEs to AstraZeneca Patient Safety until 30 days after IP is discontinued, in accordance with Section 6.4.4 (Reporting of serious adverse events). In addition, as stated in Section 6.4.3 (Recording of adverse events), any SAE or non-serious AE that is ongoing at the time defined as the end of the study, must be followed up to resolution unless the event is

considered by the investigator to be unlikely to resolve, or the patient is lost to follow-up. After the end of Part B (when the clinical database is closed), investigators should complete paper SAE forms and fax them directly to the AstraZeneca Patient Safety Data Entry site for entering onto the AZ Patient Safety database.

Last subject last visit (LSLV) for the safety & tolerability objective is calculated as 12 months duration of treatment from the LPI (ie, LSLV = LPI + 12 months).

The study is expected to start in Q4 2013 with Part A to be completed in Q3 2016 and Part B to be completed in Q3 2017.

The study may be terminated at individual study sites if the study procedures are not being performed according to GCP, or if recruitment is slow. AstraZeneca may also terminate the entire study prematurely if concerns for safety arise within this study or in any other study with olaparib.

The end of study is defined as ‘the last visit of the last patient undergoing the study’.

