6.2.3 Post study

After Part A of the study is completed, no further clinical data will be collected for this part of the study after the follow-up visit for patients who do not enter Part B. Patients will resume the regular follow-up schedule as suggested by their physician.

After Part B is completed (12 months from the date the last patient enters this part of the study), patients may continue to take olaparib (see Section 3.1). During this time, they will be seen as per their normal routine clinical schedule; it is recommended that patients are seen every 6 to 8 weeks. No clinical data will be collected other than SAEs.

Dispensing and accountability records will continue to be collected after the end of Part B for as long as patients continue to receive IP.

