6.4.3 Recording of adverse events

Time period for collection of adverse events

Adverse events (including SAEs) will be collected from the time of signed informed consent throughout the treatment period and up to and including the 30-day follow-up period in Part A. In Part B, AEs will be collected until 12 months after the last patient entered Part B, and including the 30-day follow-up period for any patients who discontinue. After the end of Part B, only SAEs will be collected.

Follow-up of unresolved adverse events

Any AEs/SAEs that are unresolved at the patient's last AE assessment (ie, 30-day follow-up visit in the study) are followed up by the investigator for as long as medically indicated. AstraZeneca or its representative retains the right to request

additional information for any patient with ongoing AE(s)/SAE(s) at the end of the study, if judged necessary.

Post follow-up adverse events

After study treatment completion (ie, after any scheduled post-treatment follow-up period has ended), there is no obligation to actively report information on new AEs or SAEs occurring in former study patients. If an investigator learns of any SAEs, including death, at any time after a patient has completed the study, and he/she considers there is a reasonable possibility that the event is causally related to the IP, the investigator should notify AstraZeneca Patient Safety or its representative.

If patients who are gaining clinical benefit are allowed to continue IP following data cut off and/or post study completion then as a minimum all SAEs must continue to be collected and reported to Astra Zeneca Patient Safety or its representative within the usual timeframe (Section 6.4.4).

Variables

The following variables will be collected for each AE:

- AE (verbatim)
- the date and time when the AE started and stopped
- the maximum CTCAE grade attained
- whether the AE is serious or not
- investigator causality rating against the IP (yes or no)
- action taken with regard to IP
- AE caused patient's withdrawal from IP (yes or no)
- outcome.

In addition, the following variables will be collected for SAEs:

- Date AE met criteria for serious AE
- Date Investigator became aware of serious AE
- AE is serious due to [reason]
- Date of hospitalisation
- Date of discharge

- Probable cause of death
- Date of death
- Autopsy performed
- Causality assessment in relation to Study procedure(s)
- Causality assessment in relation to Other medication
- Description of AE.

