12.2.3 Safety (Part A and Part B)

Safety analyses will be presented using the safety analysis set and will be done by means of descriptive statistics. Safety profiles will be assessed in terms of AEs, vital signs (including BP and pulse rate), ECG, laboratory data (clinical chemistry, haematology, and urinalysis), and physical examination.

Appropriate summaries of AEs, laboratory data, and vital signs will be produced. AEs will be summarised separately for Parts A and B of the study. Laboratory data, vital signs, physical examination, body temperature and ECG will be summarised by hepatic function group (moderate hepatic impairment, mild hepatic impairment or normal hepatic function) and by study day. Summaries will be presented for scheduled visits only. Any unscheduled assessments will be listed. The baseline value is defined as the latest result obtained prior to the start of IP.

The number of patients experiencing AEs following administration of olaparib as well as the number of AEs experienced will be summarised. Adverse events will be classified using the MedDRA system of nomenclature (preferred term and system organ class [SOC]). Adverse events reported before administration of olaparib will be listed only and be referred to as “pre-treatment.” Treatment emergence will be defined for each part of the study (A and B).

For Part A, a treatment emergent AE (TEAE) will be defined as an AE with the start date and time on or after the first dose date and time, and up to (not including) the date and time of the first dose in Part B, or up to (and including) 30 days after dosing in Part A.

For Part B, a TEAE will be defined as an AE with the start date and time on or after the first dose date and time in Part B, and up to (and including) 30 days after the last dose date in the study.

Similarly, the number of patients experiencing SAEs, OAEs, AEs that led to withdrawal, AEs that led to death and treatment-related AEs and the number of such events will be summarised by part, as applicable.

All AE data will be listed for all patients. In addition, SAEs, OAEs, and AEs that led to withdrawal or death, and treatment-related AEs will be listed.

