13.3.2 Paternal exposure

Male patients should refrain from fathering a child or donating sperm during the study and for 3 months following the last dose.

Pregnancy of the patient's partner is not considered to be an AE. However, the outcome of all pregnancies (spontaneous miscarriage, elective termination, ectopic pregnancy, normal birth or congenital abnormality) should, if possible, be followed up and documented.

The outcome of any conception occurring from the date of the first dose until 3 months after the last dose should be followed up and documented.

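### Section 9.5 closes the database at last patient in (Part B) plus 12 months, before the 30-day follow-up of patients who stop olaparib in the last weeks is complete

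*Protocol*

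**What the plan says.** **Closure.** Protocol Section 9.5 fixes the end of Part B as a calendar date, "defined as date of LPI in Part B plus 12 calendar months", and adds "At this time point, the clinical study database will close to new data". Last subject last visit for the safety and tolerability objective is put on the same date: "LSLV = LPI + 12 months". After closure the only reporting route described is a paper SAE form faxed to Patient Safety. Section 12.2.1 locks Part B on its completion and reports it in a CSR addendum.

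**Collection.** Section 6.4.3 gives the Part B rule: "AEs will be collected until 12 months after the last patient entered Part B, and including the 30-day follow-up period for any patients who discontinue". Its next sentence limits collection after the end of Part B to SAEs. Section 5.8.1 requires every new AE or SAE in the 30 calendar days after the last dose to be reported, and a visit at 30 (±7) days. Table 6 lists vital signs, ECG, haematology, chemistry, urinalysis, AEs and concomitant medication at that visit.

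**Analysis.** Section 12.2.3 counts a Part B event as treatment-emergent "up to (and including) 30 days after the last dose date in the study".

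**The concern.** For a patient who stops olaparib shortly before closure, the collection and analysis rules look past a date on which the database no longer accepts data. The site is told to hold the visit and report the events, but has nowhere to enter them unless they are serious.

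Safety and tolerability form the secondary objective, and additional safety data are Part B's stated data purpose. The follow-up laboratory results matter more than usual here. Under Section 6.4.3, deterioration in a protocol-mandated laboratory value is reported as an AE only if it meets an SAE criterion or is the reason for stopping treatment. An asymptomatic change in blood counts after the last dose may therefore appear only in the scheduled laboratory data. Section 1.1.2 names bone marrow as the primary target organ in the animal studies.

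A non-uniform follow-up window would also sit unmarked in the treatment-emergent AE tables, which present every patient as followed for 30 days.

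**Working it through.** No power or error-rate figure is involved. The check is day arithmetic on the protocol's own windows.

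**Inputs**
- Closure, day 0: LPI in Part B + 12 calendar months (Section 9.5).
- AE and treatment-emergent AE window: last dose + 30 days (Sections 5.8.1, 6.4.3, 12.2.3).
- Follow-up visit: last dose + 30 ± 7 days, that is day 23 to day 37 (Section 5.8.1, Table 6).

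**Formulas.** Let *s* be the number of days before closure on which the last dose is taken.
- End of AE window relative to closure = 30 − *s*.
- Visit relative to closure = 23 − *s* (earliest) to 37 − *s* (latest).

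Positive values fall after closure.

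| *s* | AE window ends | Visit, earliest to latest |
|---|---|---|
| 38 | −8 | −15 to −1 |
| 37 | −7 | −14 to 0 |
| 30 | 0 | −7 to +7 |
| 23 | +7 | 0 to +14 |
| 22 | +8 | +1 to +15 |
| 10 | +20 | +13 to +27 |
| 0 | +30 | +23 to +37 |

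- *s* of 37 or more: no conflict.
- *s* below 37: the visit can fall after closure while still inside its permitted window.
- *s* below 30: part of the AE window lies after closure.
- *s* of 22 or less: the visit falls after closure even at its earliest.

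**Is there a reading that reconciles the text?** The clause "and including the 30-day follow-up period for any patients who discontinue" in Section 6.4.3 could be taken to apply only as far as closure. That would fit Section 9.5 and the SAE-only sentence that follows, but Sections 5.8.1 and 12.2.3 and Table 6 would still run to 30 days or beyond without exception. Section 9.5 itself also points to an oversight. It defines the end of Part A with reference to the 30-day follow-up of the last patient to discontinue, and makes no such allowance for Part B. It defines the end of study as the last patient's last visit, which for a late stopper is later than LPI + 12 months. It also asks for ongoing non-serious AEs to be followed to resolution, yet describes only an SAE route after closure.

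**How many patients?** The protocol does not say, so an assumption is needed. Take a constant monthly stopping rate *h* and let every patient enter Part B on the LPI date. The chance of stopping in month 12 is exp(−11*h*) − exp(−12*h*). This is largest when exp(−*h*) = 11/12, giving (11/12)^11 × (1/12) = 0.384/12 = 0.032. No value of *h* gives more than 3.2%, and earlier entry lowers it. If all of the roughly 30 planned patients entered Part B, the expected number would be at most 30 × 0.032 = 0.96.

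**The case against.** The strongest reply is that the duty to collect is already written down. Sections 5.8.1 and 6.4.3 tell sites to gather AEs for 30 days after the last dose, SAEs keep flowing after closure, and Section 12.2.3 only classifies events and does not order their collection. On this view the fault is one line of wording, touches very few patients, and leaves the primary single-dose PK objective alone.

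Much of that stands. SAE reporting is not interrupted, the PK analysis is unaffected, and the numbers are likely to be small. For patients who continue olaparib past closure, SAE-only collection is a declared choice (Sections 3.1, 6.2.3 and 9.5) and no error. What does not follow is that the point is purely verbal: a duty to collect does not help if the database is closed when the data arrive.

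A reader might also infer that partner conceptions are cut off in the same way. Section 13.3.2 says "The outcome of any conception occurring from the date of the first dose until 3 months after the last dose should be followed up", while the last scheduled contact is at about 30 days, and for patients not entering Part B Section 6.2.3 says "no further clinical data will be collected for this part of the study after the follow-up visit". The documents do not support calling this a contradiction. Section 13.3.2 asks for partner-pregnancy outcomes where possible and states that such a pregnancy is not an AE, so the release from active AE and SAE reporting in Section 6.4.3 does not reach it. Section 13.3 separately requires pregnancy outcomes to be reported. An extra contact at 3 months would be a preference.

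**Conclusion.** The conflict is real and limited. For a patient whose last dose falls fewer than 30 days before LPI + 12 months, part of the required AE window lies after closure. For a last dose fewer than 37 days before it, the follow-up visit can do so too. What is lost is new non-serious AEs and follow-up laboratory, vital-sign and ECG results; SAEs are not lost.

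The number affected cannot be derived from the protocol. The ceiling of about 3% for month 12 rests on a constant stopping rate and entry on the LPI date. A cluster of stops near closure would exceed it.

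A reader might infer that those affected are mostly in the moderate impairment group, since that group is recruited last. The protocol does not show this. Entry to Part B is optional, any patient still on treatment near closure is at risk of the same truncation, and no split by group is given.

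**What to change.** In Section 9.5, separate the data cut-off from database closure. Keep LPI in Part B + 12 calendar months as the cut-off for on-treatment data, and close the database only once every patient who stopped on or before that date has completed the 30 (±7)-day follow-up. The latest such visit is 37 days after the cut-off (last dose on the cut-off date, visit at day 37).

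Align two other places with this:
- the last-subject-last-visit definition in Section 9.5, which should include the follow-up tail;
- Section 6.4.3, where the SAE-only sentence should exempt the 30-day follow-up of patients who stopped by the cut-off.

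SAE-only collection for patients who continue olaparib beyond the cut-off can stay as it is.

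The cost is a Part B lock, and hence a CSR addendum, up to about 5 weeks later (37/7 = 5.3). No visit or procedure is added, because the follow-up is already scheduled, and the Part A reports are unaffected.
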